1.0 Study Summary

Study Title	MEND 2: Making Treatment Decisions Using Genomic Testing
Study Design	Single Arm Feasibility and Efficacy Study
Primary Objective	
• Examine intervention feasibility via patient and oncologist acceptability, recruitment and retention, and fidelity
Secondary Objective(s)	
• Evaluate intervention effects on comprehension and treatment preferences.• Assess potential intervention mechanisms on comprehension, preferences, and satisfaction.
Research Intervention(s)/Investigational Agent(s)	Two surveys and audio recordings of patient-physician encounter using the question prompt list.
IND/IDE #	N/A
Study Population	Patients
Sample Size	75
Study Duration for individual participants	About a month, depending on appointment schedule.
Study Specific Abbreviations/Definitions	QPL: Question Prompt List HER2: Human Epidermal Growth Factor Receptor 2 ER: Estrogen Receptor PR: Progesterone Receptor LCCC: Lombardi Comprehensive Cancer Center WHC: Cancer Institute at Washington Hospital Center MCC: H. Lee Moffitt Comprehensive Cancer Center

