9.0 Study Timelines*

9.1 The participants will be enrolled for about a month. They will complete the first interview after consenting and will also complete a follow up interview right after receiving Oncotype DX results. All study activities should be completed within 2 months. Recruitment and retention are described in Figure 1.

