12.0 Local Number of Subjects

60

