14.0 Withdrawal of Subjects*

- 14.1 Reason for withdrawing include lack of time and not being interested in participating in research related to breast cancer.
- 14.2 N/A
- 14.3 Participants will be informed that they can withdraw from the study at any time. We will track the number of eligible participants that withdraw. Data from participants that withdraw from the study will not be used.

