17.0 Data Management* and Confidentiality

17.1 We will calculate descriptive and frequency distributions for all variables. We will assess the quality of the data and evaluate the extent and impact of missing data. For categorical variables, we will use Chi-Square tests or Fisher's exact tests if needed. We will test continuous variables with Student t-tests or Mann-Whitney U tests for non-normal data. Any variable that exhibits a $p < .10$ association with the key predictors or outcomes will be controlled in multivariable analyses. Potential covariates include sociodemographic and clinical variables as well as differenced.

Our primary endpoint is the percentage of patients activated via a question prompt list intervention. Women will demonstrate significant increase in comprehension from pre- to post-QPL.

Using a 2-tailed $\alpha = 0.05$ and assumed a minimum of 75 participants at T2 and accounting for clustering by oncologist, we calculated effective sample sizes assuming an average cluster size of 10 patients per oncologist and an ICC of 0.02. This reduces the sample size by a factor of 1.18, leaving an effective $N = 64$ at T2. We will have 80% power to detect changes in mean comprehension of 0.4 SD assuming a correlation of 0.5 between pre- and post- scores. We will use multilevel models to address the clustering of observations within patients and of patients within oncologists. These mixed effects regression models will include random effects for patient and oncologist and fixed effects for time, the main predictor, and covariates. The multilevel model for 2a will be a linear model and we will estimate the adjusted mean change in comprehension and the corresponding 95% confidence interval. We will estimate an adjusted odds ratio with the corresponding 95% confidence interval.

17.2 Data collected in this study will be used exclusively for research purposes; it will be managed and stored according to our sites' security standards for data that require the highest possible security to ensure there will be no inadvertent disclosure. Any computers storing or accessing data collected for the study will be required to comply with these standards.

During the trial, all study data downloaded from REDCap or gathered from other sources will reside in a HIPAA-compliant study folder. Access to the study folder is provided based

PROTOCOL TITLE:

Making Treatment Decisions Using Genomic Testing

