26.0 Multi-Site Research*

26.1 Study-Wide Number of Subjects*

We very conservatively project 60 eligible participants per year from LCCC/WHC and 120 eligible participants per year at MCC.

26.2 *Subjects will be recruited according to methods under the control of the local site. Sites will have bi-monthly meetings to discuss strategies and any issues as they arise.*

PROTOCOL TITLE:
Making Treatment Decisions Using Genomic Testing

References

6. NCCN Clinical Practice Guidelines. Breast Cancer. Version 4.2024 [Internet]. Available from: https://www.nccn.org/professionals/physician_gls/pdf/breast.pdf

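### Does the 80% power at 0.4 SD in section 17.1 misstate what 75 participants at T2 can detect?

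*Combined protocol and SAP*

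**What the plan says.** The power paragraph in section 17.1 uses a two-sided alpha of 0.05 and "assumed a minimum of 75 participants at T2". It allows for clustering by oncologist with 10 patients per oncologist and an ICC of 0.02, which gives a design effect of 1.18 and an effective N of 64. It then concludes: "We will have 80% power to detect changes in mean comprehension of 0.4 SD assuming a correlation of 0.5" between pre and post scores. The planned analysis is a mixed model with random effects for patient and oncologist. The method behind the power figure is not named.

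Other sections bear on the number 75:

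- Section 1.0 (Study Summary): "Sample Size 75".
- Section 9.1: "Recruitment and retention are described in Figure 1". The figure is not in the text available for review.
- Section 12.0: a local number of 60.
- Section 14.3: "Data from participants that withdraw from the study will not be used".
- Section 26.1: "We very conservatively project 60 eligible participants per year from LCCC/WHC and 120 eligible participants per year at MCC".

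**The concern.** Two things catch the eye.

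First, a pre-post correlation of 0.5 makes the SD of the change equal to the SD of the score. The calculation is then a one-sample problem with a standardized effect of 0.4 and 64 effective pairs, and that has clearly more than 80% power. A printed power that does not follow from its printed inputs suggests a wrong input, a wrong formula or an unstated method.

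Second, 75 appears both as the study's sample size and as the minimum at T2. The two agree only if nobody is lost between enrolment and T2. Yet retention is itself a feasibility outcome under Specific Aim 1, and data from participants who withdraw are dropped. If 75 is really the number enrolled, the effective N of 64 is a best case and the power for comprehension could fall below what is claimed.

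**Working it through.** **Inputs (section 17.1).** Two-sided alpha 0.05; 75 at T2; cluster size 10; ICC 0.02; pre-post correlation 0.5; change of 0.4 SD; power 80%.

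**Step 1: effective sample size.** Design effect = 1 + (10 − 1) × 0.02 = 1.18. Effective N = 75 / 1.18 = 63.6, printed as 64. Both figures reproduce.

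**Step 2: SD of the change.** SD of change = SD × √(2 × (1 − 0.5)) = 1.0 SD. A 0.4 SD shift in the mean is therefore a standardized change of 0.4.

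**Step 3: power of a paired test.** The noncentrality is 0.4 × √64 = 3.2.

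- Normal approximation: Φ(3.2 − 1.96) = Φ(1.24) = 0.893. Detectable change at 80% power = (1.96 + 0.84) / 8 = 0.350 SD.
- Noncentral t with 63 df: power 0.883. Detectable change at 80% power = 0.356 SD.

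The pair of 80% and 0.4 SD is not an exact match. To one decimal, however, 0.350 (0.3502 before rounding) and 0.356 both print as 0.4. To get exactly 80% at 0.4 SD with N = 64, the correlation would have to be about 0.37 (t) or 0.35 (normal), not the stated 0.5. Rounding of the detectable change is the simpler explanation.

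**Step 4: dependence on the method.** At 10 per oncologist, 75 patients means about 7 or 8 oncologists. If the time effect were tested on cluster-level degrees of freedom with the same N = 64, the results would be:

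| df | Power at 0.4 SD | Detectable at 80% |
|---|---|---|
| 63 (paired t) | 88.3% | 0.356 SD |
| 7 | 78.3% | 0.409 SD |
| 6 | 76.0% | 0.421 SD |

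The plan does not describe the last two rows. They show that the printed 0.4 SD is what more than one reasonable method gives at one decimal.

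**Step 5: tolerance for loss.** Under the paired t-test, 80% at 0.4 SD needs 51.0 effective pairs, and 51.0 × 1.18 = 60.2, so 61 at T2. That is 61 / 75 = 81.3%, or 18.7% fewer than 75. The T2 numbers below are illustrations, not retention rates from the documents. N is T2 / 1.18, unrounded.

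| At T2 | Effective N | Power at 0.4 SD | Detectable at 80% |
|---|---|---|---|
| 75 | 63.6 | 88.1% | 0.36 SD |
| 68 | 57.6 | 84.7% | 0.38 SD |
| 64 | 54.2 | 82.4% | 0.39 SD |
| 61 | 51.7 | 80.5% | 0.40 SD |
| 60 | 50.8 | 79.9% | 0.40 SD |
| 50 | 42.4 | 72.0% | 0.44 SD |

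**Step 6: enrolment if 75 must reach T2.** At an assumed 90% retention, 75 / 0.9 = 83.3, so 84 enrolled; at 80%, 75 / 0.8 = 93.75, so 94. Both are well below the 60 + 120 = 180 eligible patients projected per year in section 26.1.

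**The case for a change.** The best case for acting is that the two points are linked. The claim withstands plausible loss only because of a margin that section 17.1 does not report. With the method named, 0.36 SD printed and the enrolment target given apart from the T2 minimum, a reader could see a retention floor of about 61, which is useful in a study whose primary objective is feasibility. It would cost two or three sentences. The mixed model also leaves the degrees of freedom open, so calling the figure conservative depends on a method that nobody has stated.

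Part of this stands. The figure cannot be checked exactly without the method, and the readable text gives 75 in both roles with no visible allowance for loss.

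The rest does not carry. Section 17.1 does say what its 75 is: the minimum at T2. The local number in section 12.0 and the yearly eligible counts in section 26.1 do not conflict with it. Recruitment and retention are referred to Figure 1, and its absence from the extracted text cannot be held against the plan. Printing 88% or 0.36 SD would tie the plan to a paired test that it does not name, which adds precision the documents do not support.

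**Conclusion.** The concern does not call for a change. The design effect and effective N are right, and the detectable change of 0.356 SD agrees with the printed 0.4 SD at the precision used. On the plan's effective-N approach, true power at 0.4 SD is about 88%, so the stated 80% errs on the safe side. The least favourable reading tried, 6 cluster-level degrees of freedom, gives 76% and 0.42 SD, which is still 0.4 SD at one decimal.

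The double use of 75 is a small gap in the readable text. A sponsor or analyst would settle it by reading section 17.1 literally, alongside Figure 1. Even if 75 were the number enrolled, 80% power at 0.4 SD would hold down to about 61 at T2.

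This rests on a correlation of 0.5, an ICC of 0.02, clusters of 10 and a paired t-test. Naming the method or adding a decimal would be a courtesy to the reader. It would not alter enrolment, the mixed-model analysis or how a secondary comprehension result is read.

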17.3 N/A

17.4 N/A

18.0 Provisions to Monitor the Data to Ensure the Safety of Subjects*

18.1 We do not anticipate more than minimal risk to participants.

19.0 Provisions to Protect the Privacy Interests of Subjects

19.1 No one who is not a part of the study team will have access to the study records or data, unless it is necessary to reveal this information for regulatory or legal reasons. Only a code number will be used to identify study-related data. Matching lists of names and code numbers will be kept in locked storage facilities in the PI's office and/or laboratory space. All data will be similarly stored in locked facilities. All computer files containing participant data will be accessed only through password protected security systems and are stored on a secure and private server.

20.0 Compensation for Research-Related Injury

20.1 We do not anticipate more than minimal risk to participants.

21.0 Economic Burden to Subjects

21.1 n/a

22.0 Consent Process

22.1 We will obtain consent from participants prior to their first interview, QPL distribution, recorded patient-physician interaction, and follow up interview.

- Consent will be obtained verbally via phone call and physically through mailed consent form.

Non-English Speaking Subjects

- *N/A*

Waiver or Alteration of Consent Process (consent will not be obtained, required information will not be disclosed, or the research involves deception)

- We are requesting a limited HIPAA waiver to support recruitment. All information obtained for individuals who are not retained as participants will be destroyed.
- Consent will be obtained as an online consent.

Subjects who are not yet adults (infants, children, teenagers)

- *N/A*

Cognitively Impaired Adults

- *N/A*

Adults Unable to Consent

- *N/A*

23.0 Process to Document Consent in Writing

PROTOCOL TITLE:
Making Treatment Decisions Using Genomic Testing

23.1 Participants will complete verbal consent to all study activities either in clinic or over the phone. They will receive a printed copy of the consent over the mail along with a self-addressed, pre-stamped return envelope.

24.0 Setting

24.1 We anticipate recruiting from across the LCCC/MedStar clinical research (surgery and medical oncology) network. This network includes the main academic hospital and several local community referral hospitals in the metro-DC area.

Eligible breast cancer patients will also be recruited from Moffitt Cancer Center. The Clinical Research Department at MCC utilized several means to screen patients to ascertain their potential eligibility for clinical trials. This site has a central Research Department to assist and facilitate with participant recruitment as follows. This includes screening of the electronic scheduling system, review of schedules posted within clinical care areas, attendance at tumor boards, and regular interaction with physicians and nurses.

- 1) Access is sought solely to review PHI as necessary to prepare a research protocol for similar purposes preparatory research (i.e. screening),
- 2) No PHI will be removed, and
- 3) The PHI access and review is necessary for the research purposes.

25.0 Resources Available

25.1 *The study will be conducted within the context of a funded research program and supported by trained research staff. All staff will be trained to support this protocol and methods. We will collaborate with existing shared resources within the cancer center for recruitment.*

26.0 Multi-Site Research*

26.1 Study-Wide Number of Subjects*

We very conservatively project 60 eligible participants per year from LCCC/WHC and 120 eligible participants per year at MCC.

26.2 *Subjects will be recruited according to methods under the control of the local site. Sites will have bi-monthly meetings to discuss strategies and any issues as they arise.*

PROTOCOL TITLE:
Making Treatment Decisions Using Genomic Testing

References

6. NCCN Clinical Practice Guidelines. Breast Cancer. Version 4.2024 [Internet]. Available from: https://www.nccn.org/professionals/physician_gls/pdf/breast.pdf
